**Figure 1 Study Flowchart**

Abbreviations: THS 2.2 = Tobacco Heating System 2.2; CC = conventional cigarettes.

6.1.1 Timing of Confinement Period

The 9 day confinement period consists of:

- The Admission Day (Day -2).
- The run-in period, from Admission on Day -2 until 06:29 AM of Day -1.
- The baseline period, from Day -1, 06:30 AM until Day 1, 06:29 AM.
- The exposure period, from Day 1, 06:30 AM until Day 5, 11:00 PM.
- The day of Discharge, Day 6, from Day 5 (11:01 PM) to time of Discharge on Day 6.

6.2 Selection of Study Population

6.2.1 Inclusion Criteria

The following inclusion criteria will be applicable for this study:

1. Subject has signed the informed consent form (ICF) and is able to understand the information provided in the Subject Information Sheet and ICF.
2. Subject is aged from 23 to 65 years (inclusive).
3. Subject is Japanese.

4. Smoking, healthy subject as judged by the Investigator based on all available assessments from the Screening period/day of Admission.
5. Subject smokes at least 10 commercially available non-menthol CCs per day (no brand restrictions) with a maximum yield of 1 mg nicotine ISO/CC, as labeled on the cigarette package, for the last 4 weeks, based on self-reporting. Furthermore, the subject has been smoking for at least the last three consecutive years. The smoking status will be verified based on a urinary cotinine test (cotinine ≥ 200 ng/mL).
6. The subject does not plan to quit smoking in the next 3 months.
7. The subject is ready to accept interruptions of smoking for up to 5 days.
8. The subject is ready to accept using the THS 2.2.

6.2.2 Exclusion Criteria

The exclusion criteria are:

1. As per Investigator judgment, the subject cannot participate in the study for any reason.
2. A subject who is legally incompetent, physically or mentally incapable of giving consent.
3. The subject has medical condition requiring smoking cessation, or clinically relevant diseases in the judgment of the Investigator.
4. The subject has a body mass index (BMI) < 18.5 or ≥ 32 kg/m².
5. As per Investigator judgment, the subject has medical conditions which require or will require in the course of the study, a medical intervention which may interfere with the study participation and/or study results.
6. The subject has used nicotine-containing products other than commercially available CC (either tobacco-based products or nicotine-replacement therapy) as well as electronic cigarettes and similar devices, within 4 weeks prior to assessment.
7. The subject has received medication (prescribed or over the counter) within 14 days or within 5 half-lives of the drug (whichever is longer) prior to the Admission Day (Day -2) which has an impact on CYP1A2 or CYP2A6 activity.
8. If a subject received any medication (prescribed or over the counter) within 14 days prior to Screening or prior to the Admission Day (Day -2) it will be decided at the discretion of the Investigator if these can potentially interfere with the study objectives or subject's safety.
9. Concomitant use of non-steroidal anti-inflammatory drugs (NSAIDs) or acetylsalicylic acid.
10. The subject has a positive alcohol test and/or the subject has a history of alcohol abuse that could interfere with subject's participation in the study.
11. The subject has a positive urine drug test.
12. Positive serology test for human immunodeficiency virus (HIV) 1/2, hepatitis B surface antigen or hepatitis C virus.
13. Donation or receipt of whole blood or blood products within 3 months prior to Admission.

14. The subject is a current or former employee of the tobacco industry or of their first-degree relatives (parent, sibling or child).
15. The subject is an employee of the investigational site or any other parties involved in the study or of their first-degree relatives (parent, sibling or child).
16. The subject has participated in a clinical study within 3 months prior to the Screening Visit.
17. The subject has previously participated in the same study at a different time (i.e., each subject can be included in the study population only once).
18. For women only: Subject is pregnant (does not have negative pregnancy tests at Screening and at Admission), or is breast feeding.
19. For women only: Subject does not agree to use an acceptable method of contraception*.

* Intrauterine device, intrauterine system, established use of oral/injectable/implantable/transdermal hormonal methods, barrier methods of contraception (condoms, occlusive caps) with spermicidal foam/gel/film/suppository, vasectomized partner(s) or true abstinence (periodic abstinence and withdrawal are not effective methods) from Screening until the end of the safety follow-up period.

6.3 Product Allocation and Blinding

6.3.1 Methods of Assigning Subjects to Product Arms

Randomization will be conducted through the Interactive Web and Voice Response System (IXRS).

Subjects will be randomized to 1 of the 3 arms. Each sex and each of the current CC consumption levels (10-19 CC/day and >19 CC/day) will have a quota applied to ensure they represent at least 40% of the total study population.

Four separate randomization lists were provided (male smokers who smoke 10-19 CC/day, female smokers who smoke 10-19 CC/day, male smokers who smoke >19 CC/day, and female smokers who smoke >19 CC/day). Block randomization is used within each stratum (i.e., each list) in a 2:1:1 ratio (THS 2.2:CC:SA).

The randomization scheme is generated by a statistical division within [REDACTED] and none of the study team (including study sponsor and [REDACTED] investigators and study subjects will be exposed to the live randomization codes prior to randomization.

6.3.2 Blinding

This is an open-label study; therefore, the subjects and investigators will be unblinded to subject's product assignment after randomization. However, there will be a limited degree of blinding in the data review and data analysis process. In particular, PMI and [REDACTED] personnel will be blinded to the randomized product as summarized in the following table (Table 2: Blinding Scheme):

**Table 2: Blinding Scheme**

Blinded Study Personnel	End of Blinding Period
PMI and ██████ study statisticians	After the SAP finalization or database lock ¹ , whichever comes last.
PMI study data managers	After the finalization of PMI blind database review ¹ .
PMI safety and clinical scientist	After the finalization of PMI blind database review ¹ . Can be actively un-blinded before that time point in case of the occurrence of any safety question, when appropriate.

¹ As part of the PMI Quality Control (QC) activity, data listings will be reviewed by the ██████ and PMI study team before database lock, with no access to the randomization information. Full details will be available in the data review plan.

Any PMI and ██████ personnel who are not listed in the above table will be unblinded by default.

Data will not be made available from the unblinded study team to blinded study team without a dummy randomization or masking in place, and any communications among the two groups will avoid the use of subject randomization information until database lock. PMI will receive blinded data for the pre-analysis data review as planned in the data review plan.

6.3.3 Compliance to Product Allocation

Compliance for all arms will be ensured by strict distribution of the products (product by product) and collection of used THS Tobacco Sticks and the CC butts after use will be documented in appropriate logs.

In addition, in subjects in the SA arm, the compliance will be chemically verified using exhaled CO breath. The cut-off point for the CO breath test value to distinguish subjects in the SA arm with CC use vs. no CC use will be 10 ppm (Benowitz et al. 2002). No subjects from the SA arm will be withdrawn from the study if their exhaled CO breath test results are >10 ppm.

7 DERIVED AND COMPUTED VARIABLES

Mean change from baseline (baseline is defined in Section 12.1.4 “Definitions for Statistical Data Analysis”) is the mean of all individual subjects’ change from baseline values. Each individual change from baseline will be calculated by subtracting the individual subject’s baseline value from the value at the timepoint. The individual subject’s change from baseline values will be used to calculate the mean change from baseline.

Mean percent change from baseline is the mean of all individual subjects’ percent change from baseline values. Each percent change from baseline will be calculated by subtracting the individual subject’s baseline value from the value at the desired timepoint and then

dividing this calculated value by the individual subject's baseline value and multiplying by 100. These individual subjects' percent changes from baseline values will be used to calculate the mean percent change from baseline.

When the baseline value is 0, 1 will be used in the denominator for calculating the percent change from baseline.

The QT interval corrected using Bazett's formula (QTcB) will be calculated as follows:

$$QTcB = \frac{QT}{\sqrt{\left(\frac{60}{HR}\right)}}$$

The QT interval corrected using Fridericia's formula (QTcF) will be calculated as follows:

$$QTcF = \frac{QT}{\sqrt[3]{\left(\frac{60}{HR}\right)}}$$

Reported BMI will be calculated at site from the body weight and height using the following formula:

$$BMI = \frac{\text{weight in kilograms}}{\text{height in meters}^2} \quad (\text{kg/m}^2)$$

7.1 Biomarkers

Values below the Lower Limit of Quantification (LLOQ) for BoExp and risk markers will be imputed using LLOQ/2. For values above the Upper Limit of Quantification (ULOQ) i.e., preceded by a ">", for example ">xx", the numerical xx will be used for calculation and reporting in summary tables. The number of values below LLOQ or above ULOQ will be presented in each summary table.

7.1.1 Biomarkers of Exposure

The adjustment of the urinary BoExp concentration for creatinine will be calculated as:

$$\text{Biomarker (corrected for creatinine)} = \frac{[\text{Biomarker}]}{[\text{Creatinine}]}$$

where the [] indicated concentrations measured from the same 24 hour urine collection.

The quantity excreted for a BoExp over 24 hours will be calculated as:

$$\text{Quantity Excreted over 24 hours} = [\text{Biomarker}] * \text{urine volume}$$

where the concentration and the urine volume are from the same 24 hour urine collection.

7.1.2 Risk Markers

For those risk markers measured in urine an adjustment of the concentration for creatinine in urine will be calculated as:

$$\text{Risk Marker (corrected for creatinine)} = \frac{[\text{Risk Marker}]}{[\text{Creatinine}]}$$

where the concentrations are measured from the same 24 hour urine collection.

The quantity excreted for the risk markers measured in urine over 24 hours will be calculated as:

$$\text{Quantity Excreted over 24 hours} = [\text{Risk Marker}] * \text{urine volume}$$

where the concentration and the urine volume are from the same 24 hour urine collection.

7.1.3 Nicotine Equivalents

The quantity excreted of NEQ over 24 hours will be derived according to the formula below. The concentrations reported for free nicotine and its five major metabolites will not be used as analysis variables.

$$\begin{aligned} \text{NEQ [g]} &= (\text{free nicotine}_c [\mu\text{mol/L}] + \text{nicotine-glucuronide}_c [\mu\text{mol/L}] \\ &+ \text{free cotinine}_c [\mu\text{mol/L}] + \text{cotinine-glucuronide}_c [\mu\text{mol/L}] \\ &+ \text{free } \textit{trans}\text{-3'-hydroxycotinine}_c [\mu\text{mol/L}] \\ &+ \textit{trans}\text{-3'-ydroxycotinine-glucuronide}_c [\mu\text{mol/L}]) \\ &* 162.2 [\mu\text{g}/\mu\text{mol}] * \text{urine volume (L)} / 1000 [\mu\text{g}/\text{mg}] \end{aligned}$$

N.B. All concentrations must be in $\mu\text{mol/L}$ before applying the above formula.

The conversion factors will be applied as follows:

Free nicotine	The molecular weight is 162.232 g/mol (Chemical Information Specialized Information Services RN:54-11-5). Therefore to convert nicotine from ng/mL to ng/mol, the result in ng/mL is multiplied by 6.164.
Nicotine glucuronide	The molecular weight is 338.356 g/mol (Chemical Information Specialized Information Services RN:152306-59-7). Therefore to convert nicotine from ng/mL to ng/mol, the result in ng/mL is multiplied by 2.955.
Cotinine	The molecular weight is 176.218 g/mol (Chemical Information Specialized Information Services RN:486-56-6). Therefore to transform cotinine from ng/mL to nmol/L, the result in ng/mL will be multiplied by 5.675.
Cotinine-glucuronide	The molecular weight is 352.341 g/mol (Chemical Information Specialized Information Services RN:139427-57-9). Therefore to transform cotinine from ng/mL to nmol/L, the result in ng/mL will be multiplied by 2.838.
Trans-3'hydroxycotinine	The molecular weight is 192.217 g/mol (Chemical Information Specialized Information Services RN:34834-67-8). Therefore to transform trans-3' hydroxycotinine from ng/mL to nmol/L, the result in ng/mL is multiplied by 5.202.
Trans-3'hydroxycotinine-glucuronide	The molecular weight is 368.34 g/mol (Chemical Information Specialized Information Services RN:132929-88-5). Therefore to transform trans-3' hydroxycotinine from ng/mL to nmol/L, the result in ng/mL is multiplied by 2.715.

The adjustment of NEQ for creatinine in urine will be calculated as:

$$\text{NEQ (corrected for creatinine)} = \frac{[\text{NEQ}]}{[\text{Creatinine}]}$$

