2.2 Purpose of the Study

The overall goal of the study is to show that the *ad libitum* use of THS 2.2 for 5 days by adult healthy Japanese smokers results in a reduction in selected BoExp to HPHCs (except BoExp to nicotine) in a well-controlled environment and to obtain information about safety in subjects using the THS 2.2 product as compared to smokers continuing smoking their own preferred brand of CC to evaluate how similar is the reduced exposure in the THS 2.2 arm as compared to smoking abstinence. Smokers who are asked to abstain from using any nicotine/tobacco containing products will be used as a reference point. The subjects allocated to THS 2.2 and CC arms will be allowed to use their assigned product *ad libitum*.

Additional parameters will be explored on selected variables (e.g., Cytochrome P450 2A6 (CYP2A6)/Cytochrome P450 1A2 (CYP1A2) enzymatic activity, pharmacokinetic [PK] profile of nicotine and cotinine, product evaluation, product use and related subjective effects, human smoking topography, and selected risk markers).

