12.6.2 Secondary Analyses

12.6.2.1 Biomarkers of Exposure

In addition, the quantity excreted over 24 hours for MHBMA, 3-HPMA and S-PMA will be presented.

The PP Population will be used to examine the robustness of the analysis of the primary endpoints. The primary analysis on the FAS will be repeated on the PP population using the same methodology as detailed in Section 12.6.1.1 “Primary Biomarkers of Exposure in 24 hour collection”.

The primary BoExp will also be examined to compare the reductions in THS 2.2 vs. SA using the same methodology as for the primary analysis.

The secondary BoExp are exhaled CO, total 1-OHP in urine, Total NNN in urine, 4-ABP in urine, 1-NA in urine, 2-NA in urine, o-tol in urine, CEMA in urine, HEMA in urine, B[a]P in urine, HMPMA in urine, S-BMA in urine, Total NNAL in urine and NEQ in urine. The urine parameters will be expressed as concentrations adjusted for creatinine and the quantity excreted over 24 hours.

The baseline of the exhaled CO will be the time-matched measurements on Day 0, i.e. the 1st measurement on Days 1 to 5 will be matched to the 1st measurement on Day 0 and similarly for the 2nd, 3rd and 4th measurements. The baseline of the urinary biomarkers will be the last assessment prior to 06:29 AM on Day 1.

The values and percent changes for urinary BoExp in the quantity excreted over 24-hours and the concentration adjusted for creatinine will be listed and summarized. In addition line graphs will be produced for product means (and 95% CI) over all timepoints.

CO in exhaled breath will be measured using the Micro+™ Smokerlyzer® or similar device, conducted on Day -2 to Day 6. On Day -1 to Day 5 the first test per day will be performed within 15 minutes prior to the first product use and then between 12:00 and 01:30 PM, between 04:00 and 05:30 PM and between 08:00 and 09:30 PM. On Days -2 and Day 6 the CO breath tests will be conducted once.

Descriptive statistics summarized by exposure will be produced separately for all timepoints for all visits applicable for exhaled CO. This will be done on the FAS, stratified by sex, and CC consumption.

Actual values and percent changes from baseline in levels of exhaled CO will be listed and summarized. In addition line graphs will be produced for product means (and 95% CI) over all timepoints.

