15.3.3.2 Listing of Secondary Biomarkers and Sampling / Collection Times

12.6.2.1.1 Confirmatory Analysis

The hypothesis to be tested for each of the secondary BoExp is that the geometric mean level on Day 5 of the BoExp for THS 2.2 is lower relative to CC.

Analysis of the secondary BoExp will be conducted on the natural log scale. In order to test the follow hypothesis

$$\begin{aligned} \text{Null hypothesis (H}_0\text{):} & \quad m_1 \geq m_2 \\ \text{Alternative hypothesis (H}_1\text{):} & \quad m_1 < m_2 \end{aligned}$$

Where m_1 and m_2 are the geometric means of the BoExp levels on Day 5 for THS 2.2 and CC respectively.

The SAS code will be the same as described in Section 12.6.1.1 “Primary Biomarkers of Exposure in 24 hour collection”.

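### SAP 7.1.3 labels nicotine equivalents in grams although its formula gives milligrams and omits the nmol/L to µmol/L step; separately, NEQ falls under a lower-than-CC hypothesis that the protocol's aim does not extend to nicotine

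*SAP*

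**What the plan says.** **Units.** SAP 7.1.3 adds the concentrations of free nicotine and five metabolites in µmol/L, multiplies by 162.2 µg/µmol and by urine volume in litres, and divides by 1,000 µg/mg. The result is labelled NEQ [g]. A note follows: "N.B. All concentrations must be in $\mu\text{mol/L}$ before applying the above formula".

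The SAP then lists the conversion factors to apply. For free nicotine: "Therefore to convert nicotine from ng/mL to ng/mol, the result in ng/mL is multiplied by 6.164". For nicotine-glucuronide: "Therefore to convert nicotine from ng/mL to ng/mol, the result in ng/mL is multiplied by 2.955". For cotinine: "Therefore to transform cotinine from ng/mL to nmol/L, the result in ng/mL will be multiplied by 5.675". The other three rows also name nmol/L.

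The creatinine adjustment divides [NEQ] by [Creatinine]. SAP 7.1.1 uses square brackets for concentrations, but 7.1.3 derives NEQ only as a 24-hour quantity.

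**Hypothesis.** SAP 12.6.2.1 ends its list of secondary BoExp with "Total NNAL in urine and NEQ in urine". SAP 12.6.2.1.1, headed as a confirmatory analysis, states: "The hypothesis to be tested for each of the secondary BoExp is that the geometric mean level on Day 5" is lower for THS 2.2 than for CC, with H1: m1 < m2. Protocol 2.2 gives the goal as showing that use of THS 2.2 "results in a reduction in selected BoExp to HPHCs (except BoExp to nicotine"), and protocol 4.2 makes the same exception.

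**The concern.** NEQ is the trial's urinary measure of nicotine uptake. It is a secondary endpoint, both as quantity excreted and adjusted for creatinine, and it is the regressor for the risk-marker slopes in SAP 12.6.3.6.1. Section 7.1.3 is the rule a programmer will code from. It contains a wrong result unit, a missing step and two rows with an impossible unit, so two competent programmers could produce values that differ by 1,000.

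The hypothesis point is separate. If NEQ is tested with H1 lower than CC, reduced nicotine uptake would count as a hypothesis met, although the protocol's reduction aim leaves nicotine out and the nicotine objective is only to determine levels.

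**Working it through.** **1. The conversion factors.** One ng/mL equals one µg/L. Dividing by molecular weight in g/mol gives µmol/L; multiplying by 1,000 gives nmol/L. So 1,000/MW converts ng/mL to nmol/L. With the molecular weights in SAP 7.1.3:

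| Analyte | MW | 1,000/MW | SAP factor | SAP unit |
|---|---|---|---|---|
| Free nicotine | 162.232 | 6.16401 | 6.164 | ng/mol |
| Nicotine-glucuronide | 338.356 | 2.95547 | 2.955 | ng/mol |
| Cotinine | 176.218 | 5.67479 | 5.675 | nmol/L |
| Cotinine-glucuronide | 352.341 | 2.83816 | 2.838 | nmol/L |
| Trans-3'-hydroxycotinine | 192.217 | 5.20245 | 5.202 | nmol/L |
| Its glucuronide | 368.34 | 2.71488 | 2.715 | nmol/L |

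All six factors reproduce to three decimals as nmol/L. None gives µmol/L.

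**2. The result unit.** µmol/L × µg/µmol × L = µg, and dividing by 1,000 µg/mg gives mg. The [g] label does not follow.

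**3. Size, by illustration.** The concentrations and volume here are assumptions, not figures from the documents: 1,000, 500, 1,200, 2,000, 4,000 and 1,500 ng/mL in table order, and 1.5 L.

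- Sum: 6,164 + 1,477.5 + 6,810 + 5,676 + 20,808 + 4,072.5 = 45,008 nmol/L = 45.008 µmol/L.
- Note followed: 45.008 × 162.2 × 1.5 / 1,000 = 10.95, which is mg. A direct mole calculation gives 0.01095 g, the same amount. Printed as 10.95 g, the label is wrong by 1,000.
- Note not followed: 45,008 × 162.2 × 1.5 / 1,000 = 10,950, which is µg. It is 1,000 times too large if read as mg and 1,000,000 times if read as g.

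The error factors do not depend on the assumed values.

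**4. What a constant factor k changes.** SAP 12.6.2.1 analyses urinary endpoints on the log scale with log baseline as covariate. Both log terms shift by log k; the intercept absorbs this and the arm difference is unchanged. In a simulated log-scale ANCOVA, multiplying NEQ by 1, 1,000 and 1,000,000 gave the same THS 2.2:CC ratio each time (0.866, 95% CI 0.749 to 1.001, p = 0.0515). Percent change is also unchanged, since k cancels. The displayed NEQ levels scale by k. In the linear risk-marker model the NEQ slope scales by 1/k with its p-value unchanged; in the simulation it fell from 0.0585 to 0.0000585 at k = 1,000.

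**5. Where NEQ is placed.**

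| Kept apart from the reduction hypothesis | Placed with the secondary BoExp |
|---|---|
| Protocol 2.2 and 4.2: nicotine excepted from the aim | SAP 12.6.2.1: in the list that 12.6.2.1.1 then tests |
| Protocol Table S1: own class, BoExp to nicotine | Protocol 7.5.1.3: in the secondary list |
| SAP 5.2: absent from objective 1 (reduction), present in objective 3 (levels) | Table A2 footnote a, protocol and SAP |

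**The case against.** The strongest reply on units is that the note requiring µmol/L is binding. Whoever follows it gets numerically correct milligrams, and the printed µg/mg divisor shows the intended unit. The factors are right, and four of six rows, like the CYP1A2 and CYP2A6 tables in SAP 7.1.4 and 7.1.5, say nmol/L, so ng/mol is plainly a slip. This stands. A reader might infer that NEQ will be wrong by 1,000 to 1,000,000. The documents do not support that: the larger figure needs the note to be ignored and the [g] label to be taken literally. Nor is the THS 2.2 versus CC comparison at risk. That would need the two ng/mol rows to be handled differently from the other four, and nothing in the SAP suggests it.

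The missing m in [g] could be a text-extraction fault, since the same formula has lost a letter from hydroxycotinine. The label should be checked against the source PDF. The unwritten division and the two ng/mol rows do not depend on it.

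On the hypothesis, protocol 7.5.1.3 and the Table A2 footnote already list NEQ as secondary, so it would be wrong to infer that the SAP alone departed from the protocol, and the silence of SAP Section 9 carries little weight. The wording of 12.6.2.1.1 does not name NEQ, NEQ is outside the success criterion in SAP 5.5.2, and two-sided 95% CIs are already planned. A reader might also take the remark in protocol 2.1.2 on nicotine delivery paralleling CC as a trial aim. It is product background, not an objective or hypothesis.

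What remains is that 12.6.2.1 defines the secondary BoExp by a list that includes NEQ, and the hypothesis applies to each of them.

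**Conclusion.** Both parts hold, at modest size. Section 7.1.3 has a result label wrong by 1,000, an unwritten division by 1,000 and two rows with an impossible unit. With the note followed, only the label is wrong. With the factors used directly, values are in µg, a further factor of 1,000. Reported NEQ levels and the NEQ slopes in SAP 12.6.3.6.1 are exposed. Log-scale ratios, percent changes and p-values are not, provided all six analytes are scaled alike. No primary endpoint, alpha or sample size is affected.

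The undefined [NEQ] is a related gap: inserting the 24-hour quantity would leave each subject's urine volume in the creatinine-adjusted endpoint. The bracket convention in SAP 7.1.1 points to a concentration, so this needs a definition rather than a new method.

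NEQ should not sit under a one-directional reduction hypothesis, given the protocol's stated aim, Table S1 and SAP objective 3. The inconsistency is shared by both documents and bears on interpretation of one secondary endpoint.

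**What to change.** In SAP 7.1.3:
- label the result NEQ [mg/24 h];
- write nmol/L in the two nicotine rows;
- state that the factors give nmol/L and that the values are divided by 1,000 before the formula;
- define [NEQ] for creatinine adjustment as the molar sum in µmol/L × 162.2 / 1,000, in mg/L (in the illustration, 45.008 × 162.2 / 1,000 = 7.30 mg/L).

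In SAP 12.6.2.1 and 12.6.2.1.1, take NEQ out of the secondary BoExp reduction hypothesis and report its Day 5 THS 2.2:CC ratio with two-sided 95% CI under secondary objective 3. Align protocol 7.5.1.3 and the Table A2 footnotes in both documents.

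The cost is wording and one line of derivation code, with no change to data or design.
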